12. STATISTICAL METHODS AND SAMPLE SIZE DETERMINATION

12.1 Description of analysis sets

12.1.1 Safety analysis set

All subjects who receive at least one dose of investigational product and for whom any postdose data are available will be included in the safety analysis set.

12.1.2 Pharmacokinetic analysis set

The PK analysis set will include all healthy subjects who took at least one dose of AZD8931 and have at least one postdose PK measurement without important protocol deviations or violations thought to significantly affect the PK of the investigational product. Data from healthy subjects with deviations determined to affect PK will be excluded from the PK analysis set. A strategy for dealing with data affected by protocol violations and deviations will be agreed by the study team physician, pharmacokineticist, and statistician, prior to clean file and code break.

12.1.3 Interim pharmacokinetic analysis

Not applicable.

12.2 Methods of statistical analyses

The statistical analysis will be performed at

, using Standard Operating Procedures and Work Instructions.

Given the exploratory nature, no formal statistical hypothesis testing will be performed in this study.

Missing data will result in a reduced sample size for the parameter. Since the statistical analyses will be predominantly descriptive presentations in tables and individual data listings, no action will be taken to handle missing data.

A healthy subject who withdraws prior to the last planned observation in a study period will be included in the analyses up to the time of discontinuation.

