3.1 Overall study design and flow chart

This is an open label, single dose study conducted at a single study centre in 6 healthy male subjects. All subjects will receive a single dose of $[^{14}C]$ AZD8931 on Day 1.

The study will consist of 3 visits. Visit 1, Screening will take place within 28 days before Visit 2, Day 1. Visit 2 will be the residential period when each subject will be resident in the study centre for 11 days from Day -1 until Day 11 (240 hours postdose). Visit 3, Follow-up will occur 5 to 10 days after the last sample has been collected.

The study flow chart is presented in Figure 1 and the study assessments in Table 1.

Figure 1 Study flow chart

[figure not shown]

Table 1Study assessments

Visit	Visit 1 (screening)		sit 2 ial period)	Visit 3 (Follow-up)
Day	≤28 days before Visit 2	Day -1	Days 1-11	5-10 days after last sample collection
Inclusion/exclusion criteria	Х			
Informed consent	Х			
Demographic data	Х			
Medical history	Х			
Drugs of abuse and alcohol urine screen	X°	Х		
Serology for hepatitis and HIV	Х			
Height and weight measurements	Х			X^n
Admission to study centre		Х		
Dosing			\mathbf{X}^{f}	
Discharge from study centre			X^{g}	
Adverse event recording	Х	Х	Х	Х
Concomitant medications	Х	Х	Х	
Vital signs ^a	Х		X^h	Х
12-Lead electrocardiogram	Х		X^h	Х
Safety clinical laboratory evaluations	Х	Х	X^{i}	Х
Physical examination	Х			Х
Ophthalmology	Х			Х
Blood sample for pharmacogenetics (optional)	X ^e			
Blood sampling for total radioactivity count and AZD8931 and its metabolite (if feasible) concentration ^b			$\mathbf{X}^{\mathbf{j}}$	
Blood sampling for metabolite profiling			X^k	
Urine sampling for total radioactivity count and metabolite profiling ^c			X^l	
Faeces sampling for total radioactivity count and metabolite profiling ^{c,d}			X^m	

^a Supine blood pressure and pulse.

^b Additional collections of blood samples (5.7 mL) at 24-hour intervals may cease if no radioactivity is detected in 2 consecutive plasma samples.

^c Additional 24-hour collection of urine and/or faeces may continue until 90% total recovery is achieved or recovery in urine/faeces in the 24-hour period is less than 1% of the total administered dose of radioactivity.

Clinical Study Protocol Drug Substance AZD8931 Study Code D0102C00007 Edition Number 1.0 Date

- ^d Toilet paper (first 2 wipes) collected for the first 48 hours postdose.
- ^e Timing of sample collection at the discretion of the study centre.
- f Day 1 (0 hours).

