- ^g Day 11 (after the 240 hours postdose sample has been collected).
- ^h Predose, 24 hours postdose, and Day 11.
- ⁱ 24 hours postdose, and Day 11.
- ^j Predose, 1, 2, 4, 6, 8, 12, 24, 48, 72, 96, 120, 144, 168, 192, 216, and 240 hours postdose.
- ^k 1, 4, 6, 12, and 24 hours postdose.
- ¹ Predose (-12 to 0 hours), 0 to 6, 6 to 12, 12 to 24, 24 to 48, 48 to 72, 72 to 96, 96 to 120, 120 to 144, 144 to 168, 168 to 192, 192 to 216, and 216 to 240 hours postdose.
- ^m Predose (-48 to 0 hours), 0 to 24, 24 to 48, 48 to 72, 72 to 96, 96 to 120, 120 to 144, 144 to 168, 168 to 192, 192 to 216, and 216 to 240 hours postdose.
- ⁿ Weight only.
- ^o Drugs of abuse only.
- HIV: human immunodeficiency virus

If a subject vomits within 2 hours of dosing, the vomit should be retained for radioactivity analysis.

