7. BIOLOGICAL SAMPLING PROCEDURES

7.1 Volume of blood

The total volume of blood that will be drawn from each subject in this study is presented in Table 3.

Assessment		Sample volume (mL)	No. of samples	Total volume (mL)
Safety	Clinical chemistry	5	5	25
	Haematology	2	5	10
	Serology	3.5	1	3.5
Pharmacokinetic determination of AZD8931 and o-desmethyl AZD8931 (if applicable) concentrations in plasma		3	17	51
Whole blood total radioactivity		2	17	34
Plasma total radioactivity		2	17	34
AZD8931 metabolite profiling		10	5	50

Table 3Volume of blood to be drawn from each subject

Assessment		Sample volume (mL)	No. of samples	Total volume (mL)
Safety	Clinical chemistry	5	5	25
	Haematology	2	5	10
	Serology	3.5	1	3.5
Pharmacogenetics		10	1	10
Total				217.5

Table 3Volume of blood to be drawn from each subject

Additional collections of blood may continue at 24-hour intervals until radioactivity counts are <3 times the background count on 2 consecutive samples. However, the maximum volume to be drawn from each subject will not exceed 500 mL, ie, the same volume as would be drawn during a regular blood donation.

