12.2.3 Pharmacokinetics

A listing of PK blood sample collection times as well as derived sampling time deviations will be provided. A listing of urine and faeces sample collection start and stop times will be provided. A subject listing of all whole blood, plasma, urine, and faeces radioactivity-time data, as well as plasma AZD8931 and o-desmethyl AZD8931 concentration-time data will be presented.

Pharmacokinetic variables will be summarized by matrix (blood, plasma, urine, and faeces) and analyte (AZD8931, o-desmethyl AZD8931, and radioactivity) using appropriate descriptive statistics (eg, n, arithmetic mean, SD, and coefficient of variance [CV] %, geometric mean, and geometric CV [GCV], minimum, median, and maximum). The geometric mean is calculated as the exponential of the arithmetic mean calculated from data on a log scale. The GCV is calculated as $100\% \cdot \sqrt{(\exp(s^2)-1)}$ where s is the SD of the data on a log scale. Graphical presentations of PK variables will be used as appropriate.

The ratio of plasma AZD8931 concentration versus plasma radioactivity, the ratio of plasma o-desmethyl AZD8931 concentration versus plasma radioactivity, and the ratio of whole blood radioactivity versus plasma radioactivity will be calculated at each time point for each subject.

Plasma concentrations below the lower limit of quantitation (LLOQ) will be handled as follows:

- At a time point where at least one value is above LLOQ but less than or equal to 50% values below LLOQ, all values below LLOQ are set to LLOQ and a mean (arithmetic and geometric) value and SD and CV (%) are calculated
- At a time point where more than half of the observations are below LLOQ only individual values are reported; mean, SD, geometric mean, and CV (%) will be set to not quantifiable (NQ). The minimum value and the median are set to less than LLOQ
- If all values are below LLOQ at any time point no descriptive statistics are calculated for that time point. Write not applicable (NA) in the field for SD and CV (%) and write less than LLOQ in fields for mean, geometric mean, minimum, median, and maximum in the table
- The number of observations greater than LLOQ (number of observations above LLOQ [N>LLOQ]) will be reported in the table

Figures of geometric mean radioactivity-time and concentration-time data will be presented on linear and semi-logarithmic scales by dosing regimen. Individual subject radioactivity-time

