12.3 Determination of sample size

This is a Phase I study to investigate the metabolism, excretion, and PK of $[^{14}C]$ AZD8931 in man and the number of subjects is based on the desire to gain adequate information whilst exposing as few subjects as possible to the study medication and procedures. Therefore 6 subjects will be recruited for this study.

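### If collection runs past 240 h, by-time group means rest on men selected by their own results: upward bias for blood, plasma and interval excretion, downward for cumulative recovery

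*Protocol*

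**What the plan says.** Protocol Section 3.1, Table 1, schedules blood for every man at "Predose, 1, 2, 4, 6, 8, 12, 24, 48, 72, 96, 120, 144, 168, 192, 216, and 240 hours postdose". The urine and faeces intervals also end at 240 h. Collection after that is optional and depends on results:

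- Blood, Table 1 note b: "Additional collections of blood samples (5.7 mL) at 24-hour intervals may cease if no radioactivity is detected in 2 consecutive plasma samples".
- Blood, Section 7.1: "Additional collections of blood may continue at 24-hour intervals until radioactivity counts are <3 times the background count on 2 consecutive samples".
- Urine and faeces, Table 1 note c: 24-hour collection "may continue until 90% total recovery is achieved or recovery in urine/faeces in the 24-hour period is less than 1" per cent of the administered dose.

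For values that are not there, Section 12.2 says "Missing data will result in a reduced sample size for the parameter" and adds that "no action will be taken to handle missing data". Section 12.2.3 plans the by-time display: "Figures of geometric mean radioactivity-time and concentration-time data will be presented on linear and semi-logarithmic scales by dosing regimen". It names no last time point. Its LLOQ rules apply to plasma concentrations that were measured and fell below the limit. The exclusion of extra measurements from descriptive statistics stands in Section 12.2.2, which covers safety. Section 12.3 sets the size: "Therefore 6 subjects will be recruited for this study".

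**The concern.** Up to 240 h each by-time mean is planned over the same six men. After 240 h, whether a man gives a sample depends on the quantity being measured. A man whose plasma radioactivity has fallen away may stop, and a slow eliminator goes on. With no rule beyond a smaller n, a mean at 264 h would be the mean of the slow eliminators, joined on the same curve to a six-man mean at 240 h.

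The excreta rule selects in two ways. The 1% arm removes men who now excrete little per day. The 90% arm removes men whose cumulative recovery is already high. So the mean amount per interval is pushed up, while mean cumulative recovery is generally pushed down.

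The primary objective is to describe absorption, metabolism, excretion and PK, and the analysis is descriptive throughout. A late plateau or rise in the mean radioactivity curve could be read as slow elimination or redistribution. A low late mean recovery could be read as incomplete mass balance. Either could come from the change in who is sampled.

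**Working it through.** The protocol gives no figure to reproduce: n = 6 is justified in words and no half-life is stated. The direction can be checked with an example and the possible size with a simulation. All levels, half-lives and recoveries below are assumptions.

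**Example, blood.** Suppose levels at 264 h are 1, 1.2, 1.5, 2, 5 and 8 times background, with a common half-life of 96 h.

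- Levels at 240 h are higher by 2^(24/96) = 1.189, and at 216 h by 2^(48/96) = 1.414.
- The first four men are at 1.41, 1.70, 2.12 and 2.83 at 216 h, and at 1.19, 1.43, 1.78 and 2.38 at 240 h. All are below 3 on two consecutive samples, so under Section 7.1 they may stop. The other two (7.07 and 11.3, then 5.95 and 9.51) go on.
- Six-man geometric mean at 264 h: (1 × 1.2 × 1.5 × 2 × 5 × 8)^(1/6) = 144^(1/6) = 2.3. At 240 h: 2.29 × 1.189 = 2.7.
- Geometric mean of the two men sampled at 264 h: √(5 × 8) = 6.3.

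The plotted curve goes from 2.7 up to 6.3 while every man falls; the true six-man value is 2.3. The arithmetic means at 264 h are 6.5 (two men) and 18.7/6 = 3.1 (all six).

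The NQ rule does not prevent this. If it were applied to radioactivity with those four men below LLOQ at 240 h, the 240 h mean would be NQ. At 264 h both remaining men are quantifiable, so a mean would reappear.

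**Example, excreta.** The same four men stop at 240 h because they have reached 90%.

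- Recovery in 240–264 h of 0.2, 0.3, 0.4, 0.6, 1.5 and 2.0% of dose: all six 5.0/6 = 0.83%; last two 3.5/2 = 1.75%. Too high.
- Cumulative recovery at 264 h of 94, 93, 92, 91, 82 and 78%: all six 530/6 = 88.3%; last two 160/2 = 80.0%. Too low by 8.3 points.
- Carrying forward the stopped men's 240 h values (93.8, 92.7, 91.6, 90.4) gives 528.5/6 = 88.1%, only 0.2 points below the six-man value.

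**Simulation.** 20,000 sets of six men per scenario; mean of men still collected against mean of all six at 264 h, in sets where one to five men remain. Assumptions: starting level 100 times background, 10% assay noise, stopping rules applied as mandatory, with the Section 7.1 limit for blood. Ratios are medians.

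| Blood: half-life, CV | Sets with 1–5 men left | Arithmetic mean ratio | Geometric mean ratio |
|---|---|---|---|
| 30 h, 30% | 54% | 3.2 | 9.6 |
| 30 h, 50% | 79% | 2.9 | 21 |
| 48 h, 30% | 93% | 1.4 | 2.0 |
| 48 h, 50% | 95% | 1.5 | 3.6 |
| 72 h, 30% | 25% | 1.2 | 1.5 |
| 72 h, 50% | 60% | 1.2 | 1.8 |

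The bias was upward in essentially all of these sets. The largest geometric ratios should not be taken at face value. With a 30 h half-life the typical man at 264 h is at 100 × 2^(−264/30) = 0.22 times background, a comparison level that would not in practice be measured.

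| Excreta: half-life, mean final recovery (CV 40%) | Interval ratio | Cumulative difference, points | Cumulative biased down |
|---|---|---|---|
| 30 h, 85% | 2.9 | −2.1 | 80% of sets |
| 30 h, 95% | 3.0 | −4.7 | 99.9% |
| 48 h, 85% | 1.5 | −1.8 | 91% |
| 48 h, 95% | 1.7 | −4.2 | 99.9% |
| 72 h, 85% | 1.2 | −1.7 | 98% |
| 72 h, 95% | 1.2 | −3.0 | 100% |

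Interval means were biased upward in at least 99.5% of sets.

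A second blood simulation (40,000 studies per scenario) assumed a median half-life of 48–96 h with CV 20–30%, level CV 30%, and 33–67% of men below the limit at 240 h. It gave a geometric mean ratio of 1.2 to 2.5. The plotted mean was higher at 264 h than at 240 h in 46–96% of studies in which some but not all men stopped.

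**The case against.** The strongest reply is that nothing says times after 240 h will enter a group table or mean curve. The last scheduled time in every matrix is 240 h, discharge follows that sample, and a collection never planned for a man is not plainly missing data. The time range of a figure is the kind of detail an SAP settles. Section 3.2 also expects almost all radioactivity to have been excreted by the end of sampling, so any tail should be small. Individual profiles are plotted, data are listed, and n is reported, so a mean resting on two men would be visible.

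Much of this stands. The problem arises only if collection is extended and those times are summarised, and treating stopped men as missing is an inference from the lack of any other rule. But the protocol does plan for extension, and it does state a rule for absent values. That rule behaves badly when absence is caused by the outcome. Reporting n shows that the group shrank; it does not correct the curve.

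A reader might infer several stronger points that the documents do not support:

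- That every group mean after 240 h is too high. Cumulative recovery goes the other way, because one arm of note c stops men whose recovery is high.
- That late samples come only from men above the limits. The text says collection may cease or may continue.
- That the main results are biased. AUC, half-life, Ae and fe are derived from each man's own data (Section 11.2), and the smaller-n rule drops no stopped man from them.

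**Conclusion.** The concern holds in a conditional form. If collection goes past 240 h and later times are summarised over the men still sampled, by-time means of blood and plasma radioactivity and of per-interval excretion are biased upward, and a mean curve can rise while every man declines. Mean cumulative recovery is biased downward, by 1.7 to 4.7 points in the scenarios tried.

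The blood and interval directions held in every scenario. The sizes are not a property of this trial: geometric mean ratios ran from 1.2 to 2.5 under one set of assumptions and from 1.5 to 21 under another, because the protocol gives no half-life. The effect is confined to by-time group summaries after 240 h.

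Separately, note b (no radioactivity detected) and Section 7.1 (below 3 times background) give different blood limits. They need reconciling, since the limit decides who is still sampled.

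**What to change.** Add to Section 12.2.3: by-time descriptive statistics and geometric mean figures are limited to the scheduled times up to 240 h; later samples are listed, plotted individually and used in each subject's own parameters. This removes both directions of bias and discards no data.

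If a group value after 240 h is wanted, keep all six men in it. Count men stopped under the blood rule as below the limit for blood and plasma radioactivity, and carry forward the last cumulative value for recovery. The below-limit device should not be used for excreta, because a man stopped at 90% recovery is not below any limit.

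Reconcile the blood limits in Table 1 note b and Section 7.1. The cost is a sentence or two; the small downside is that the mean curve ends at 240 h.

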12.2.1 Subject characteristics

Continuous variables will be summarized using descriptive statistics (n, mean, standard deviation [SD], minimum, median, and maximum). Categorical variables will be summarized in frequency tables (frequency and proportion).

12.2.2 Safety and tolerability

All safety data (scheduled and unscheduled) will be presented in the data listings. Continuous variables will be summarized using descriptive statistics (n, mean, SD, minimum, median, and maximum). Categorical variables will be summarized in frequency tables (frequency and proportion). Graphical presentations will be used as appropriate. Examples may include line graphs showing individual or mean development over time, and shift plots showing pretreatment values on horizontal axis and posttreatment values on vertical axis.

Extra measurements (such as unscheduled or repeat assessments) will not be included in the descriptive statistics, but will be included in subject listings. All AEs, ECG outliers, and clinical laboratory outliers that occur following the first dose of investigational product will be included in the tabulations of AEs and outlier events, including episodes that occur at unscheduled evaluations or during the washout period between treatments.

All AEs will be collected for each subject from the time when informed consent is obtained (Visit 1) until the follow-up visit. Adverse events that occur before dosing will be reported separately.

Adverse events will be summarized by preferred term and system organ class using MedDRA nomenclature system (Version 12.0 or higher) by groups and treatments. Furthermore, listings of SAEs and AEs that led to discontinuation will be made and the number of volunteers who had any AEs, SAEs, AEs that led to discontinuation, and AEs with severe intensity will be summarised.

Tabulations and listings of data for vital signs, clinical laboratory tests, ECGs, and physical examination findings will be presented. Where applicable, data will be summarized for the absolute value at each scheduled assessment and for the corresponding change-from-baseline. For clinical laboratory tests, listings of values for each healthy subject will be presented with abnormal or out-of-range values flagged. Shift tables will be presented for laboratory values. Clinical laboratory data will be reported in Système International units in the Clinical Study Report. Exceptions to this recommendation are enzyme data (common examples are liver function tests alanine aminotransferase, aspartate aminotransferase, gamma-glutamyltransferase) for which IU/L may be used rather than the Système International unit ukat/L.

For ECG parameters, the QT correction factor will be based on the Fridericia's formula. Further categorical summaries of absolute QT and QTcF values (more than 450 ms, more than

480 ms, and more than 500 ms) and change from predose values in QT and QTcF values (more than 30 ms, and more than 60 ms) will also be produced.

12.2.3 Pharmacokinetics

A listing of PK blood sample collection times as well as derived sampling time deviations will be provided. A listing of urine and faeces sample collection start and stop times will be provided. A subject listing of all whole blood, plasma, urine, and faeces radioactivity-time data, as well as plasma AZD8931 and o-desmethyl AZD8931 concentration-time data will be presented.

Pharmacokinetic variables will be summarized by matrix (blood, plasma, urine, and faeces) and analyte (AZD8931, o-desmethyl AZD8931, and radioactivity) using appropriate descriptive statistics (eg, n, arithmetic mean, SD, and coefficient of variance [CV] %, geometric mean, and geometric CV [GCV], minimum, median, and maximum). The geometric mean is calculated as the exponential of the arithmetic mean calculated from data on a log scale. The GCV is calculated as $100\% \cdot \sqrt{(\exp(s^2)-1)}$ where s is the SD of the data on a log scale. Graphical presentations of PK variables will be used as appropriate.

The ratio of plasma AZD8931 concentration versus plasma radioactivity, the ratio of plasma o-desmethyl AZD8931 concentration versus plasma radioactivity, and the ratio of whole blood radioactivity versus plasma radioactivity will be calculated at each time point for each subject.

Plasma concentrations below the lower limit of quantitation (LLOQ) will be handled as follows:

- At a time point where at least one value is above LLOQ but less than or equal to 50% values below LLOQ, all values below LLOQ are set to LLOQ and a mean (arithmetic and geometric) value and SD and CV (%) are calculated
- At a time point where more than half of the observations are below LLOQ only individual values are reported; mean, SD, geometric mean, and CV (%) will be set to not quantifiable (NQ). The minimum value and the median are set to less than LLOQ
- If all values are below LLOQ at any time point no descriptive statistics are calculated for that time point. Write not applicable (NA) in the field for SD and CV (%) and write less than LLOQ in fields for mean, geometric mean, minimum, median, and maximum in the table
- The number of observations greater than LLOQ (number of observations above LLOQ [N>LLOQ]) will be reported in the table

Figures of geometric mean radioactivity-time and concentration-time data will be presented on linear and semi-logarithmic scales by dosing regimen. Individual subject radioactivity-time

and concentration-time data will be graphically presented on linear and semi-logarithmic scales. Additional graphical presentations of PK data may be added at the discretion of the pharmacokineticist.

